2.8.5 Vital signs

Absolute values and change from baseline will be summarized for vital sign parameters by visit, time point, treatment group and Part. For SBP and DBP, average of 3 readings will be used for analysis while all 3 readings will be provided in the listing. Baseline and change from baseline in height, weight, and BMI will be assessed with/without using age- and sex-adjusted z-scores and summarized by visit treatment group and Part.

The number and percentage of patients meeting clinically notable criteria at any time, considering all data collected after first dose of double-blind treatment, from scheduled, unscheduled, and premature discontinuation visits will be summarized by treatment group and Part. The worst post-baseline value in each part will be used for this analysis. Notable criteria are defined in Appendix 5.6. Clinically notable criteria will be met when both of the following occur:

- Post-baseline value meets the clinically notable criteria.
- Baseline value does not meet the clinically notable criteria.

The baseline value is the last value prior to and up to Day 1 of the double-blind treatment.

All vital signs data will be listed by treatment group, participant, and visit/time and if clinically notable criteria are met, abnormalities will be flagged.

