6.7.2 Instruction for prescribing and taking study treatment

Investigational and control drugs will not be dispensed to the participants. Study drug injections will be performed exclusively at the study site by qualified clinical study site staff under the supervision of the investigator or designee.

The site of injection is the abdomen, alternating sides for each injection. Injections should not be done into areas of active skin disease or injury such as sunburns, skin rashes, inflammation, tattoos or skin infections.

Participants will be administered one s.c. injection of study drug at pre-defined visits as specified in the Assessment Schedule (Table 8-1) and summarized below.

- **Part 1:** Each participant will receive one injection of blinded inclisiran or placebo on Day 1, a second injection of blinded inclisiran or placebo on Day 90 and a subsequent injection of blinded inclisiran or placebo on Day 270 ("6 months dosing").
- **Part 2:** Participants randomized to placebo in Part 1 will receive a single injection of blinded inclisiran on Day 360, while participants randomized to inclisiran in Part 1 will receive a single injection of blinded placebo on Day 360. All participants will receive subsequent doses of open-label inclisiran on Day 450 and Day 630.

Injections will be administered after all other study assessments have been completed for the visit. At the Randomization (Day 1) and Day 360 visits, vital signs (blood pressure and pulse) and ADA (Day 1 only) will be assessed a second time 4 hours after injection.

Participants must be observed in the clinic for at least 4 hours post injection on Day 1 and Day 360 (i.e. first dosing of inclisiran) and for at least 30 minutes post injection for all other dosing visits before being discharged.

Should a participant develop signs or symptoms of anaphylaxis when study drug is injected, the investigator will need to collect a blood sample for tryptase within 30 minutes of the onset of anaphylaxis (or as soon as possible).

All kits of study treatment assigned by the IRT will be recorded in the IRT system.

All injections to the participant as well as study drug interruptions/discontinuations (i.e. no injection at a designated dosing visit) during the study must be recorded on an appropriate eCRF.

7 Informed consent procedures

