LDL-apheresis recording (if applicable)	x	x	х	x	х	х	х	х	x	х	х	х	
Fasting LDL-C	Х	Х		Х	Х	Х	Х	Х	Х	Х	Х	Х	
Fasting PCSK9		Х		Х	Х		Х	Х		Х		Х	
Full fasting lipid / lipoprotein profile ⁹		Х			х		х	х		х		Х	
Anti-drug antibodies ¹⁰		Х			Х		Х			Х		Х	
Full chemistry ¹¹		Х					Х					Х	
Limited chemistry ¹¹	Х		Х	Х	Х	Х		Х	Х	Х	Х		
Hematology	Х	Х	Х		Х		Х		Х	Х		Х	
Sexual hormones		Х					Х					Х	
Urinalysis	Х	Х	Х		Х		Х		Х	Х		Х	
AEs/SAEs	Х	Х	Х	Х	Х	Х	Х	Х	Х	Х	Х	Х	
Injection site reaction assessment		Х	х	х	х	х	х	х	х	х	x	Х	

Novartis	
Amended Protocol Version 02 (Clean)	

Confidential

Period	Screening ¹		Part 1 (D	ouble-bl	ind, place	bo-contro	lled)		Part 2 (Open-labe	l, single-a	arm)	Follow-up
Visit Name	Screening	Day 1 (Baseline & 1st Treatment)	Day 30	Day 90	Day 150	Day 270	Day 330	Day 360 ("Switch Day") ²		Day 510	Day 630	Day 720 (End of Treatment/ Study) ³	Safety follow-up (last visit +30 days)⁴
Days	-28	1	30	90	150	270	330	360	450	510	630	720	750
Neurological Examination		х					х					Х	
Tanner staging / menarche		х			х		х			х		х	
Safety Follow up Call ¹⁴													S

X Assessment to be recorded in the clinical database or received electronically from a vendor

S Assessment to be recorded in the source documentation only

¹ Screening / run-in period

² Day 360 ("Switch Day") is a shared visit, i.e. the end of Part 1 and the start of Part 2 of the study

³ For participants who prematurely discontinue the study for any reason [e.g. if a participant's parent(s)/legal representative(s) / a participant (if applicable) decide to prematurely and permanently discontinue the participant from study treatment and decline further follow-up visits] an EOS visit should also be scheduled as soon as possible.

⁴ 30 days after the last study visit or 90 days after the last administration of study drug, whatever is longer

⁵ Only in females of child-bearing potential (prior to study treatment administration, if applicable)

⁶ On Day 1 and Day 360 vital signs will be measured prior to injection and 4 hours post injection; at all other visits, vital signs will be measured only once (prior to injection, if applicable).

⁷ Participants will be observed in the clinic for at least 4 hours post injection on Day 1 and Day 360 and for at least 30 minutes post injection for all other dosing visits. ⁸ For any suspected episode of anaphylaxis, the investigator will need to collect a blood sample for tryptase within 30 minutes of an onset of anaphylaxis (or as soon as possible).

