2.1.1 General definitions

Study day

Study day will be defined as the number of days since the date of first dose of double-blind treatment. The date of first dose of double-blind treatment will be defined as Day 1 and the day before the first dose of study drug will be defined as Day -1.

Novartis	For business use only	Page 18
SAP amendment 4		CKJX839C12301

Therefore, for a particular date, study day will be calculated as follows:

For dates on or after the first date of double-blind treatment,

Study day = Assessment date – Date of first dose of double-blind treatment + 1;

For dates prior to the first date of double-blind treatment,

Study day = Assessment date – Date of first dose of double-blind treatment.

In case, participant has been randomized but has not received double-blind treatment then randomization visit day will be considered as Day 1.

Baseline definition

In general, for both Part 1 and Part 2, baseline value is defined as the last measurement collected on or prior to the first dose of double-blind treatment.

Post-baseline measurement

Post-baseline values are defined as those measurements that were collected after the first dose of double-blind treatment.

When change from baseline is of interest the following formula will be used for each scheduled visit and time-point where baseline and post-baseline values are both available:

Absolute change from baseline = post-baseline value – baseline value.

Percent change from baseline = (post-baseline value - baseline value) / baseline value*100.

Reflexive LDL-C

The endpoints involving LDL-C will use a reflexive LDL-C approach. The calculated LDL-C will be utilized unless triglycerides are greater than 400 mg/dL and/or calculated LDL-C is less than 40 mg/dL, in which case beta quantification LDL-C (i.e., LDL_C directly measured by ultracentrifugation) will be additionally performed and used for the analysis.

VLDL-C

The endpoints involving VLDL-C will follow the same approach as reflexive LDL-C.

Re-derivation of age-strata for mis-stratified participants

If any subject will be mis-stratified for age-group during randomization, collected age of that participant will be used to re-derive the correct age-strata at analysis level and will be used for all analyses, as needed.

Discontinuation visit mapping

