2.8 Safety analyses

In general, for Part 1 safety analyses, the SAF will be used; for Part 2 safety analysis, the OAS will be used.

Safety summaries will include only treatment emergent adverse events (TEAEs) by Part. For Part 1, TEAEs are defined as adverse events (AEs) starting on or after the first dose of doubleblind treatment or AEs that were present prior to start of double-blind treatment but increased in severity in Part 1. For Part 2, TEAEs are defined as AEs starting after the Day 360 dosing time or AEs that were present prior to the Day 360 dosing time but increased in severity in Part 2. For Part 1, if the AE start date is the same as the date of the first dose of double-blind treatment but the time is not available for comparison, the AE will be considered as treatment but the time is not available for comparison, the AE will be considered as treatment but the time is not available for comparison, the AE will be considered as treatment but the time is not available for comparison, the AE will be considered as treatment but the time is not available for comparison, the AE will be considered as treatment but the time is not available for comparison.

Vital signs values that have complete data and time values will be assigned to pre- or post-dose assessment (as per protocol) based on the actual date/time. For values with missing date/time, the scheduled visit date and time will be used. This rule will be applied to data from scheduled visits only. If a measurement scheduled as pre-dose is actually performed post-dose, or vice versa, the data will not be used for visit/time point summary.

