2.8.3 Laboratory data

Laboratory data consist of hematology, biochemistry, sexual hormones, urinalysis measurements and ADA (see Section 2.8.6). Absolute values and change from baseline will be summarized for continuous laboratory parameters by visit and box plots will also be provided by visit. Frequency table of results for categorical laboratory parameters will be presented by visit. This analysis will be performed by treatment group and Part.

Shift tables using the low, normal, high/low, or high classification (except for eGFR and HbA_{1c} where the categories outlined below will be applied) will be used to compare baseline to the worst on-treatment value by treatment group and Part. All data collected after first dose of

Novartis	For business use only	Page 31
SAP amendment 4		CKJX839C12301

double-blind treatment, from scheduled, unscheduled, and premature discontinuation visits in each part will be used to determine the worst on-treatment value.

The following categories will be used for eGFR and HbA1c:

- For eGFR, the categories will be <30 mL/min/1.73m²; ≥ 30 to <60 mL/min/1.73m²; ≥ 60 to <90 mL/min/1.73m²; and ≥90 mL/min/1.73m².
- For HbA_{1c}, the categories will be <5.7%; $\ge 5.7\%$ to <6.5%; and $\ge 6.5\%$.

The shift table dealing with the fasting plasma glucose parameter will require the lab sample to be taken fasting. Samples taken while the subject was not fasted will not be analyzed.

For selected laboratory tests, the number and percentage of patients meeting the clinically notable criteria at any time, considering all data collected after first dose of double-blind treatment, from scheduled, unscheduled, and premature discontinuation visits, will be summarized by laboratory parameter and treatment group and Part. The worst post-baseline value will be used for this analysis. Notable criteria are defined in Appendix 5.5. Clinically notable criteria will be considered met when both of the following occur:

- Post-baseline value meets the clinically notable criteria.
- Baseline value does not meet the clinically notable criteria.

Furthermore, the number and percentage of participants meeting notable criteria in liver function tests (LFT) will be summarized by treatment and Part considering on-treatment data from scheduled, unscheduled, and premature discontinuation visit. LFT criteria are defined in Appendix 5.5.

The baseline value is the last value prior to the first dose of double-blind treatment.

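### SAP 2.8.5 ties the vital-sign baseline to Day 1 and not to the first dose, so read literally it admits the 4-hour post-injection blood pressure and pulse as baseline

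*SAP*

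**What the plan says.** SAP 2.8.5 (Vital signs) gives its own baseline rule, placed directly after the two conditions for a clinically notable value: "The baseline value is the last value prior to and up to Day 1 of the double-blind treatment".

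Four other places bear on it.

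- **Meaning of Day 1.** SAP 2.1.1: "The date of first dose of double-blind treatment will be defined as Day 1". Day 1 is therefore a calendar date that includes time before and after the injection.
- **Timing of readings.** Protocol Table 8-1, footnote 6: "On Day 1 and Day 360 vital signs will be measured prior to injection and 4 hours post injection". Protocol 6.7.2 agrees: "vital signs (blood pressure and pulse) and ADA (Day 1 only) will be assessed a second time 4 hours after injection".
- **General definitions.** SAP 2.1.1 says that, in general, the "baseline value is defined as the last measurement collected on or prior to the first dose of double-blind treatment". It then adds: "Post-baseline values are defined as those measurements that were collected after the first dose of double-blind treatment".
- **Parallel laboratory rule.** SAP 2.8.3: "The baseline value is the last value prior to the first dose of double-blind treatment".

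SAP 2.8 also says that vital signs with complete date and time "will be assigned to pre- or post-dose assessment (as per protocol) based on the actual date/time". It does not say which of the two classes supplies the baseline.

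**The concern.** Vital signs have a scheduled repeat after the dose on Day 1, so a baseline rule tied to the day does not pick out a unique pre-treatment value. Taken at its word, the rule in 2.8.5 lands on the later of the two Day 1 readings, which is a post-treatment value.

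Two outputs are exposed. The first is the notable-value count, where a participant counts only if the baseline is not already notable; a wrong baseline can remove or add people. The second, if the sentence reaches that far, is the change-from-baseline summary. It is reported by time point, and so has a separate entry for the Day 1 4-hour reading.

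**Working it through.** The plan states no figure to reproduce here. The check applies each baseline rule to the protocol's order of readings: screening, Day 1 before injection (write *X_pre*), Day 1 at 4 hours (*X_4h*), later visits (*X_v*).

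**Step 1: which reading does each rule select?**

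| Rule | Anchor | Reading selected |
|---|---|---|
| SAP 2.1.1, baseline and post-baseline definitions together | first dose | *X_pre* |
| SAP 2.8.3 wording, applied to vital signs | first dose | *X_pre* |
| SAP 2.8.5 read as a date rule, Day 1 included | Day 1 | *X_4h* |
| SAP 2.8.5 read subject to the 2.1.1 post-baseline definition | first dose | *X_pre* |

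The third and fourth rows are two readings of the same sentence, and they disagree.

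**Step 2: internal consistency of 2.8.5.** Its notable-value analysis uses all data collected after the first dose as post-baseline. That includes *X_4h*. On the date reading, *X_4h* is both the baseline and a post-baseline value in the same two-condition test.

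**Step 3: effect on the notable count.** A participant counts if a post-baseline value is notable and the baseline is not. Take the upper diastolic limit in SAP Table 5-3, above 90 mmHg, with illustrative readings:

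| *X_pre* | *X_4h* | Later | Pre-dose baseline | 4-hour baseline |
|---|---|---|---|---|
| 84 | 92 | 94 | counted (84 not notable) | not counted (92 notable) |
| 92 | 84 | 94 | not counted (92 notable) | counted (84 not notable) |

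The error can go either way. In Part 1 the first pattern loses the participant even without a later notable value, because *X_4h* is itself post-baseline. The second pattern needs a notable value later. In Part 2 both patterns need a notable value in that part. If *X_pre* and *X_4h* are on the same side of the limit, nothing changes.

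**Step 4: effect on change from baseline, if the sentence governs it.**

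- At Day 1, 4 hours: *X_4h* − *X_4h* = 0 for everyone with that reading.
- At a later visit: *X_v* − *X_4h* = (*X_v* − *X_pre*) − (*X_4h* − *X_pre*). Each later change is shifted by the participant's own 4-hour change. The difference between arms is shifted only by the difference between arms in mean 4-hour change.
- For the Day 360 pair, both readings are measured against the same baseline, so the difference between them is unaffected.

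**Step 5: scope.** Protocol 6.7.2 limits the repeat vital signs to blood pressure and pulse. Height, weight and BMI, also reported in SAP 2.8.5, have no 4-hour repeat, so both readings of the rule give them the same baseline.

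**The case against.** The best defence is that a pre-dose baseline is plainly intended. SAP 2.1.1 sets the boundary at the first dose for both parts and places the 4-hour reading after it. SAP 2.8 sorts vital signs into pre- and post-dose and keeps values taken on the wrong side of the dose out of the visit and time-point summaries. SAP 2.8.5 itself uses the first dose as the start of post-baseline data. A change from baseline at 4 hours is informative only against the pre-dose value. A reading that makes a section contradict itself is the weaker one.

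This stands as evidence of intent, so it would be too strong to infer that the SAP chooses the 4-hour reading; it permits that reading. But intent does not repair the rule. SAP 2.1.1 presents its definition as the general case, which leaves room for a section-specific exception, and 2.8.5 can be taken as one. The sorting rule in 2.8 never names the baseline. A programmer working from the one sentence that defines the vital-sign baseline could take the 4-hour value.

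Three further inferences are tempting and not supported:

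- **That every vital-sign change from baseline is affected.** The sentence follows the notable-value conditions, as its counterpart in 2.8.3 does, and may govern that analysis only. Change from baseline would then stay under 2.1.1.
- **That an acute effect of the first dose would be hidden.** Absolute values are summarized by time point and arm, and all readings are listed with notable values flagged, so both Day 1 readings remain visible.
- **That about 141 participants would have wrong results.** SAP 1.1 gives 141 as the number enrolled. It is an upper limit on those with a 4-hour reading, not the number whose notable status would change.

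**Conclusion.** Wrong as written; minor. The vital-sign baseline in SAP 2.8.5 is anchored to a date on which readings are scheduled on both sides of the dose. Its literal meaning conflicts with SAP 2.1.1, SAP 2.8.3 and the post-baseline data rule in 2.8.5.

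The notable count for blood pressure and pulse can change only for participants whose two Day 1 readings straddle a limit, under the further conditions in Step 3. The documents give no data from which to estimate how many that is. The zero 4-hour change and the shift at later visits follow only if the sentence also governs the change-from-baseline summaries, which the text leaves open. These are descriptive safety summaries: no hypothesis test and no primary or key secondary result depends on them.

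The conclusion assumes that the sentence is applied literally and that the 4-hour reading was obtained. If the programming already uses the pre-injection reading, the defect is in the wording alone.

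**What to change.** Replace the baseline sentence in SAP 2.8.5 with the one in SAP 2.8.3: "The baseline value is the last value prior to the first dose of double-blind treatment". For Day 1 blood pressure and pulse this gives the pre-injection reading, and it brings the section into line with 2.1.1.

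Then confirm that the programmed baseline flag for vital signs selects the pre-injection reading, for both the notable-value and the change-from-baseline outputs. The SAP is reproduced in a clinical study report appendix, so outputs may already exist. They need rerunning only if the flag took the 4-hour value.

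The cost is one sentence and one programming check. No data collection, sample size or efficacy analysis changes.

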2.8.6 Immunogenicity

Number and percentage of subjects with treatment-induced transient and persistent ADA and no treatment-induced ADA will be summarized. Listing will be provided.

Treatment-induced ADA will be defined as a negative ADA sample at baseline and at least one positive ADA sample post-baseline. Persistent will be defined as negative ADA at baseline and confirmed positive ADA on 2 or more timepoints where the first and last were separated by a period of at least 16 weeks or positive ADA at the last timepoint or at a timepoint less than 16 weeks before an ADA negative last sample. Transient will be defined as treatment-induced ADA detected at only 1 time point post-baseline, or 2 or more sampling time points where the first and last ADA-positive samples are separated by a period less than 16 weeks, and the subject's last sampling time point is ADA-negative.

Novartis	Confidential	Page 37 of 48
Clinical Study Report Appendix 16.1.9, v1.0		Study No. CKJX839C12301

Novartis	For business use only	Page 36
SAP amendment 4		CKJX839C12301

In addition, further ADA details will be assessed and will be listed in a separate ADA report. If applicable, additional analyses may be conducted.

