8.4.1.1 Anti-drug antibodies

Serum samples for the analysis of formation of ADA will be collected at the time points detailed in the Assessment Schedule (Table 8-1).

On Day 1, ADA serum samples will be collected prior to injection and 4 hours after injection. At all other visits, one sample only will be collected.

The results from ADA after the first administration of study drug until the Day 360 visit must be blinded to participants, investigator staff, persons performing the assessments, and the CTT.

Instructions to be followed regarding sample collection, numbering, processing and shipment are outlined in a Laboratory Manual.

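### The ADA sample taken 4 hours after the first injection counts as post-baseline, so a positive there is labelled treatment-induced and can turn a transient response into a persistent one

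*SAP*

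**What the plan says.** **Sampling.** Protocol 8.4.1.1: "On Day 1, ADA serum samples will be collected prior to injection and 4 hours after injection". It continues: "At all other visits, one sample only will be collected". The ADA row of the Assessment Schedule (Protocol Table 8-1) places those later samples at Days 150, 330, 510 and 720.

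**Post-baseline.** SAP 2.1.1: "Post-baseline values are defined as those measurements that were collected after the first dose of double-blind treatment". No minimum time after the dose is set.

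**Baseline.** The general rule in SAP 2.1.1 is that "baseline value is defined as the last measurement collected on or prior to the first dose of double-blind treatment". SAP 2.8.3 says "Laboratory data consist of hematology, biochemistry, sexual hormones, urinalysis measurements and ADA", and for laboratory data it puts the baseline strictly before the first dose.

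**Classification (SAP 2.8.6).**
- Treatment-induced: "Treatment-induced ADA will be defined as a negative ADA sample at baseline and at least one positive ADA sample post-baseline".
- Persistent: negative at baseline, with either confirmed positives at two or more timepoints, the first and last "separated by a period of at least 16 weeks", or a positive at the last timepoint or within 16 weeks of a negative last sample.
- Transient: one post-baseline positive, or positives spanning under 16 weeks, with a negative last sample.

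Nothing shown takes the 4-hour sample out of these rules. SAP 2.8 does have a rule assigning vital signs, also repeated 4 hours after the Day 1 injection, to pre-dose or post-dose. ADA has no counterpart.

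**The concern.** The label treatment-induced is meant to capture antibodies that arise because of exposure. Four hours after a first exposure is too early for that, so a positive there after a negative pre-dose sample more plausibly reflects the assay than an induced response. The rule as written counts it all the same.

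The sample also starts the 16-week clock on Day 1. A participant with one real positive at a later visit and a negative last sample should be transient. A confirmed positive at 4 hours makes that participant persistent.

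ADA measurement is part of a secondary safety endpoint (Protocol Table 2-1), and Protocol 1.1 describes immunogenicity potential as low. When few cases are expected, a handful of wrong labels could visibly change the reported incidence or the transient/persistent split.

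**Working it through.** The documents state no ADA figure to reproduce. The check applies the SAP 2.8.6 rules to the sampling schedule, then sizes the effect under a stated assumption.

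**1. Spacing.** 16 weeks = 112 days. On nominal days:
- 4-hour sample to Day 150: 150 − 1 = 149 days (21.3 weeks)
- Day 150 to 330: 180 days (25.7 weeks)
- Day 330 to 510: 180 days (25.7 weeks)
- Day 510 to 720: 210 days (30.0 weeks)

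Every gap exceeds 112 days. On schedule, a confirmed 4-hour positive plus any later confirmed positive always meets the spacing criterion.

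**2. All patterns.** Take a participant negative before the dose and positive at 4 hours, with positives treated as confirmed, and classify with and without the 4-hour sample.

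| Later samples | Without 4-hour sample | With 4-hour sample |
|---|---|---|
| All negative | No treatment-induced ADA | Treatment-induced, transient |
| One positive at Day 150, 330 or 510; Day 720 negative | Transient | Persistent |
| All other patterns | Persistent | Persistent |

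Over the full schedule there are 2⁴ = 16 patterns: 1 of the first kind, 3 of the second and 12 of the third, so 4 of 16 change class. In Part 1 (Days 150 and 330) 2 of 4 change: both negative (none to transient), and Day 150 positive with Day 330 negative (transient to persistent).

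**3. Off schedule.** If the 4-hour sample is the only post-dose sample, a positive there is also the last timepoint and is classed as persistent on its own. If a negative last sample falls before Day 113, a single 4-hour positive meets both the persistent and the transient wording.

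**4. Illustrative size, Part 1.** Assumptions:
- n = 94 on inclisiran: 2/3 of the 141 enrolled (SAP 1.1), with all samples taken.
- No true antibody response.
- Independent errors with false-positive rate f = 1% to 5% per sample, after any confirmation step. This rate is assumed; the documents give none.

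Labelled treatment-induced solely because of the 4-hour sample (baseline negative, 4-hour positive, Days 150 and 330 negative): n·f·(1−f)³
- f = 0.01: 94 × 0.01 × 0.9703 = 0.91
- f = 0.05: 94 × 0.05 × 0.8574 = 4.03

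Switched from transient to persistent (baseline negative, 4-hour and Day 150 positive, Day 330 negative): n·f²·(1−f)²
- f = 0.01: 94 × 0.0001 × 0.9801 = 0.009
- f = 0.05: 94 × 0.0025 × 0.9025 = 0.21

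As a proportion, f·(1−f)³ is 1.0% to 4.3%. With the same f in both arms it is the same on placebo.

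**The case against.** The case against giving this weight has several parts.

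- **No evidence that it happens.** There is no false-positive rate, no interference data and no 4-hour positivity rate. A reader might infer that incidence is overstated; the documents support only that it could be. This stands.
- **Arms.** Protocol 4.2 says inclisiran leaves plasma within 24 to 48 hours, so drug is expected in the 4-hour sample on inclisiran only. A reader might infer a bias against inclisiran. Nothing shown says whether drug in the sample raises, lowers or leaves unchanged the assay reading, and the classification rule is the same in both arms. That inference is not supported.
- **Pre-existing antibody.** This should mostly show in the pre-dose sample, which must be negative, so it is a weak explanation for a 4-hour positive.
- **Confirmation.** The persistent spacing criterion requires confirmed positives, which should remove some assay errors. The treatment-induced definition in the same section carries no such word.
- **Independence.** Samples from one person 4 hours apart, the first negative, are unlikely to have independent errors. The illustration may be generous.
- **Separate ADA report.** SAP 2.8.6 refers further detail to it, and the schedule's ADA footnote is cut off in the text available. Either could bear on the 4-hour sample, but no rule from them is shown. The planned listing would also let an isolated Day 1 positive be traced.

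These points limit the size of the problem. None changes how the written rule classifies a 4-hour positive.

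**Conclusion.** The point holds. Followed as written, SAP 2.1.1, 2.8.3 and 2.8.6 give the wrong label in two situations: a 4-hour positive alone becomes treatment-induced transient on the full schedule, and a confirmed 4-hour positive plus one later confirmed positive becomes persistent although the last sample is negative.

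The size is unknown. The illustrative 0.9 to 4.0 participants of 94 rests on the assumed 1-5% rate, independence and the 2/3 split of 141. Switches caused purely by false positives would be rare, about 0.01 to 0.2 participants; genuine later responders would add to that by an amount the documents do not allow one to estimate.

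A secondary ambiguity points to the same fix. If the general baseline wording in SAP 2.1.1 were programmed by calendar date, the 4-hour sample could become the baseline, and a positive there would remove the participant from the treatment-induced count. The post-baseline definition and the laboratory baseline in 2.8.3 argue against that reading, but 2.8.6 does not settle it.

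The consequence is confined to a descriptive safety table. It should not be read as touching the primary or key secondary tests. This is a minor, worthwhile correction.

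**What to change.** Add to SAP 2.8.6 that the pre-dose Day 1 sample is the ADA baseline, and that the Day 1 4-hour sample is excluded from the treatment-induced, transient and persistent definitions and reported separately by arm. Check that the separate ADA report follows the same rule.

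The cost is a sentence or two in the SAP and a small programming change, with no new data. If Part 1 tables have already been produced, a footnoted re-tabulation is enough and can be recorded with the post-hoc analyses already documented at the front of the SAP appendix.
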